## 5.0 Enrollment/Randomization

The study will be conducted at the Vanderbilt University Medical Center. Institutional Review Board approval and written informed consent will be obtained from all study subjects.

We propose to study a total of 200 subjects controlled for race (50% African Americans, 50% Caucasians) and gender (50% female, 50% male). Subjects will be recruited from the Outpatient Clinics at VUMC (including the General Medicine Clinic and the Hypertension Clinic), as well as by emails, flyers, and other recruitment tools. All participants will have a baseline assessment, as well as on-going monitoring, of their health status as documented in their medical record.

[figure not shown]
Subjects will be randomly assigned to one of the study arms (diet, spironolactone, chlorthalidone, or placebo). Randomization will be determined using a stratified permuted-block randomization method. Stratification will be based on gender and race.

One treating physician will be unblinded as to whether subjects are receiving spironolactone or chlorthalidone and will guide decisions regarding subjects who develop abnormal serum potassium levels.

To specifically address Aims 1, 3 and 4, we will also enroll subjects who will only complete visits through Week 0. In addition, to aid data analysis, we will also re-enroll subjects who will complete a follow-up visit consisting of a blood draw.

## 6.0 Study Procedures

The design is a randomized, double-blind (except for those in the diet group), placebo-controlled study. Once the subject is determined to be eligible, we will randomly assign him/her to one of the study arms (diet, spironolactone, chlorthalidone, or placebo) as depicted in **Figure 1**. Each subject will be treated for 8 weeks. During the study, subjects will receive (1) a diet containing 6 g salt per day, (2) oral administration of spironolactone (50 mg per day), (3) oral administration of chlorthalidone (25 mg/day) or (4) oral administration of matching placebo. All medications and matching placebo will be prepared and dispensed by Vanderbilt's Investigational Drug Services (IDS). Except for the diet arm, the investigators and the study subjects will be blinded to the treatment. NaMRI, Pulse wave velocity (PWV) and a hyperinsulinemic euglycemic clamp (HEGC) study will be performed at the beginning and at the end of the study. An optional DNA blood sample may also be collected.

**Figure 1: Study Protocol**

**Safety Precautions:** In this protocol we have the following safety precautions: (1) Anti-hypertensive/diuretic medications (like the ones used in this study) may lower blood pressure excessively and/or alter serum electrolyte levels. Accordingly, we will monitor blood pressure and electrolyte levels throughout the study. Subjects who develop electrolyte imbalance will receive an electrolyte supplement or be asked to slightly change their diet. (2) Since the use of diuretics during pregnancy introduces unnecessary risk, female subjects will have a urine pregnancy test at each study visit before any research procedures are performed. (3) Since the presence of any metal introduces unnecessary risk, a screening X-ray exam will be performed to confirm the absence of any metal in subjects where that is a possibility.

**Permanent stopping criteria:** A patient will be terminated from the study for any of the following reasons:

- Persistent hyperkalemia ( $K > 5.5$  mmol/L) occurs;
- Any allergies to the drugs develop;
- Women who become pregnant;
- There are any adverse events or clinical events that the PI judges increases the risk to the patient;
- There are any signs or symptoms of decline or deterioration of their health status.

**Screening Visit:** Within about two weeks up to the start of the Treatment Phase (which begins after the Baseline Visits) and after the subject has provided informed consent, the following information will be collected:

- Demographics
- Medical history
- Concomitant medications

Also, the following procedures and assessments will be performed:

- Vital signs (including blood pressure)
- Physical exam

- CMP (comprehensive metabolic panel) unless there is a documented CMP within 1 month of the stipulated study entry date as part of routine medical care
- Pregnancy test
- X-ray exam

**Baseline Visits (Week 0):** Subjects that qualify for the study will be randomized to one of the study arms, and will be asked to come in a fasted state on two separate days (preferably consecutive but no more than about 4 weeks apart) to the General Clinical Research Center (GCRC). On one of the visits, a hyperinsulinemic euglycemic clamp (HEGC) study will be performed. At the other visit, NaMRI and pulse wave velocity (PWV) will be performed, as well as a hand grip test. These procedures are described below.

At the Baseline Visits, the following information will be collected:

- Concomitant medications (medication reconciliation)
- Medical history and concurrent illnesses

Also, the following procedures and assessments will be performed:

- Pregnancy test
- Vital signs (including blood pressure)
- CMP (including electrolytes)
- Blood samples for research labs, which include hsCRP, IL-6, TNF $\alpha$ , F2-isoprostanes, ADMA, s-ICAM, s-VCAM, insulin, leptin, adiponectin, resistin, C-peptide, lipid panel, FFA, and immune cell analysis
- Urine samples for research labs

Subjects in the diet arm will be counseled on the details of the low salt diet. Subjects in the other arms will be dispensed study drug. After the second Baseline visit, the intervention phase of the study begins.

**Week 2 Visit:** At the Week 2 Visit, subjects will be asked to come to the GCRC. The following information will be collected:

- Concomitant medications
- Adverse Events (AEs)

Also, the following procedures and assessments will be performed:

- Pregnancy test
- Vital signs (including blood pressure)
- CMP (including electrolytes)
- Urine samples for research labs
- Dietary counseling for those in the diet arm

**Week 4 Visit:** At the Week 4 Visit, subjects will be asked to come to the GCRC. The following information will be collected:

- Concomitant medications
- Adverse Events (AEs)

Also, the following procedures and assessments will be performed:

- Pregnancy test
- Vital signs (including blood pressure)
- CMP (including electrolytes)
- Urine samples for research labs
- Dietary counseling for those in the diet arm
- Study drug dispensing for those in the other arms

**Week 8 Visits:** At the Week 8 Visit, subjects will be asked to come in a fasted state on two separate days (preferably consecutive but no more than about 4 weeks apart) to the GCRC. On one of the visits, a hyperinsulinemic euglycemic clamp (HEGC) study will be performed. At the other visit, NaMRI and pulse wave velocity (PWV) will be performed, as well as a hand grip test. These procedures are described below.

- Concomitant medications
- Adverse Events (AEs)

Also, the following procedures and assessments will be performed:

- Pregnancy test
- Vital signs (including blood pressure)
- Physical exam
- CMP (including electrolytes)
- Blood samples for research labs, which include hsCRP, IL-6, TNF $\alpha$ , F2-isoprostanes, ADMA, s-ICAM, s-VCAM, insulin, leptin, adiponectin, resistin, C-peptide, lipid panel, FFA, and immune cell analysis
- Urine samples for research labs

**Diet Recalls:** For subjects in the diet arm, study dietitians will conduct dietary recalls via telephone interviews after the Screening Visit, as well as at Week 4 and at Week 8 to confirm compliance with the low-salt diet. We will utilize a two-day diet recall that includes one week day and one weekend day to capture variability in eating. Dietary recall data will be collected and analyzed using Nutrition Data System for Research. For subjects in the other arms, dietitians will conduct the dietary recalls 2 times—after the Screening Visit and at Week 8.

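### Persistent potassium above 5.5 mmol/L ends participation, but no potassium limit governs entry or the first dose, and a first high value on treatment has no required recheck

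*Combined protocol and SAP*

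**What the plan says.** **The stop.** Section 6.0, Permanent stopping criteria, opens: "A patient will be terminated from the study for any of the following reasons". The first of its five items is "Persistent hyperkalemia", with a limit of K > 5.5 mmol/L. It does not say how many readings make a value persistent, or how far apart they should be. Another item is a general judgement clause: "There are any adverse events or clinical events that the PI judges increases the risk to the patient".

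**Entry.** Section 4.0 sets numeric limits for eGFR and transaminases but none for potassium. A metabolic panel is part of screening "unless there is a documented CMP within 1 month of the stipulated study entry date", in which case the routine-care result stands in. No potassium value is named as acceptable.

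**Randomization and first dose.** The baseline text of Section 6.0 reads: "Subjects that qualify for the study will be randomized to one of the study arms, and will be asked to come in". Two fasting visits are planned. A metabolic panel is drawn at Week 0, and then: "Subjects in the other arms will be dispensed study drug". Treatment begins after the second baseline visit.

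**On treatment.** Panels are scheduled at Weeks 2, 4 and 8. The Week 4 list includes "Study drug dispensing for those in the other arms", again without reference to a result. Safety Precautions adds: "Subjects who develop electrolyte imbalance will receive an electrolyte supplement or be asked to slightly change their diet".

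**Who decides.** Section 5.0 gives one unblinded physician the decisions for subjects in whom abnormal potassium develops. Section 7.0 says that a subject whose electrolyte imbalance persists may be withdrawn, which is weaker than the Section 6.0 stop.

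**The concern.** One arm receives a mineralocorticoid receptor antagonist, and the protocol itself treats potassium above 5.5 mmol/L as unsafe if it persists. A limit strict enough to end participation would normally also be checked before the first dose. Here it is not, although the measurements needed are already scheduled.

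Potassium is the only laboratory value with its own numeric stopping limit, yet it has no entry limit, while renal function and transaminases do. The protocol also knows how to make a result a condition: a pregnancy test must come before research procedures at each visit. Potassium has no such step before dosing.

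What is at stake is the safety of individual participants: starting spironolactone with potassium already high, or continuing it for weeks after a first high reading that nobody is required to repeat.

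**Working it through.** There is no plan figure to reproduce. The check compares the provisions and then does some date arithmetic.

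**1. Is potassium limited before dosing?**
- Inclusion criteria (Section 4.0): 3 listed, 0 name potassium.
- Exclusion criteria (Section 4.0): 13 listed, 0 name potassium. The nearest are eGFR below 45, antihypertensives other than calcium channel blockers and beta blockers, and diabetes on drug treatment.
- Randomization: it follows qualification, so the only potassium value sure to exist by then is from screening or from the routine-care panel accepted in its place. Neither has a limit.
- Dispensing (Section 6.0): 2 points, Weeks 0 and 4; 0 depend on a potassium result.

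So a subject with K > 5.5 mmol/L at screening or Week 0 meets every written criterion and may be given spironolactone 50 mg/day. The stop is not restricted to the treatment period, so high values at both screening and Week 0 could be read as persistent. A single high value could not.

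**2. How long can a first high value go unrepeated?** Scheduled panels on treatment are at Weeks 2, 4 and 8.
- First high at Week 2: (4 − 2) × 7 = 14 days to the next scheduled panel.
- First high at Week 4: (8 − 4) × 7 = 28 days, which is 28/56 = 50% of the treatment period and ends when treatment ends.
- High at both Week 2 and Week 4: two consecutive scheduled results exist, so the stop can be applied at Week 4 with half of treatment left.

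A required repeat would bring the second reading forward as follows. The interval is an assumption.

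| Repeat within | Sooner after Week 2 | Sooner after Week 4 |
|---|---|---|
| 1 day | 14 − 1 = 13 days | 28 − 1 = 27 days |
| 3 days | 14 − 3 = 11 days | 28 − 3 = 25 days |
| 7 days | 14 − 7 = 7 days | 28 − 7 = 21 days |

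**3. How many people?** The spironolactone arm is about 41 (Section 10.0) to 200/4 = 50 (Section 5.0, if all 200 are randomized equally). Each percentage point of hyperkalemia in that arm would be 41 × 0.01 = 0.41 to 50 × 0.01 = 0.50 subjects. This gives scale only, because the documents state no rate.

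**4. Do the two withdrawal statements agree?** Section 6.0 requires termination for persistent hyperkalemia. Section 7.0 permits withdrawal for persistent electrolyte imbalance. The second may have been meant for other electrolytes, but as worded it includes high potassium, so staff have two rules for one event.

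**The case against.** The strongest reply is that several protections already exist.

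- **Population.** The renal, antihypertensive and diabetes exclusions remove many people prone to high potassium. This stands and is why the number affected is probably small. Even so, eGFR from 45 upward and ages up to 80 are allowed, and potassium supplements are not mentioned.
- **Unblinded physician.** Leaving on-treatment potassium decisions to a named role looks deliberate, and that physician could order an early repeat. This also stands, and taken alone the undefined word *persistent* would be closer to missing detail. But the role covers values that develop in the study, not clearly those present at entry, and no recheck is required.
- **Clamp.** Potassium is measured every 30 minutes during the clamp, and one clamp falls within the Baseline Visits. A reader might infer from the dispensing text that nobody sees a potassium value before treatment. That would be wrong for anyone who has the clamp. Those readings, however, guide potassium replacement while insulin is lowering it, and they set no entry limit.
- **General judgement.** The investigator can stop anyone judged to be at increased risk (Sections 6.0 and 8.0). This is real but weak for a silent laboratory finding: Section 8.0 assesses safety by interview and allows fourteen days for adverse events to reach the investigator.

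A reader might also infer that after any high Week 4 value the scheduled tests cannot trigger the stop before treatment ends. The schedule does not support that: if Week 2 was also high, Week 4 can itself show persistence. The 28-day gap belongs only to a first high value at Week 4.

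**Conclusion.** The point holds and should be fixed. Followed as written, the protocol lets a subject already above its own potassium stopping limit be randomized and given spironolactone, and only clinical judgement stands in the way. On treatment, a first high value at Week 2 or Week 4 has no required recheck for 14 or 28 days respectively, and Sections 6.0 and 7.0 disagree on whether withdrawal is compulsory.

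The conclusion rests on the written text. The study diagram is not shown, but no passage points to a potassium limit there. The number of people affected cannot be estimated from the documents. A reader might infer from the gaps that harm is likely or common; nothing in the documents supports a rate. Nor does the point bear on the primary endpoint or its analysis. The case for acting is that a potentially serious event is foreseeable and that prevention is cheap, using panels already scheduled and a limit already chosen.

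**What to change.** - **Section 4.0, new exclusion:** serum potassium above 5.5 mmol/L on the screening panel, or on the routine-care panel used in its place. This acts before randomization.
- **Section 6.0, Baseline Visits:** do not start study drug until the Week 0 potassium has been reviewed and is not above 5.5 mmol/L. If it is above, repeat within about 3 days (an assumption; range 1 to 7). If the repeat confirms it, do not start drug, apply the existing stop, and report such cases by arm. The rule is the same for spironolactone, chlorthalidone and placebo, so the hold does not reveal allocation.
- **Section 6.0, Permanent stopping criteria:** repeat any on-treatment value above 5.5 mmol/L within about 3 days, with drug held meanwhile at the unblinded physician's direction, and terminate if confirmed. Say that this includes Week 4, before further drug is taken.
- **Section 7.0:** make the withdrawal wording for persistent hyperkalemia match Section 6.0.

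The cost is a protocol amendment, an occasional unscheduled blood draw, a short dispensing delay for anyone held, and possibly a few losses after randomization. Drawing the Week 0 panel on the first of the two baseline days would let the result be seen before the second and limit the delay. Endpoints and analyses stay as they are.

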**Standard Methods (all performed for research purposes only):**

[figure not shown]
**MRI Measurements of tissue Na+ content (Primary Endpoint):** We will quantify Na+ and water content in skin and muscle by Na MRI and H MRI as reported previously using a 3.0 T Phillips Achieva scanner, equipped with a double resonant H/Na coil and a mono resonant Na coil from Rapid, Germany. This will take about an hour.

**Aortic Pulse Wave Velocity (PWV):** This test will show us the stiffness of the arteries. This test will be measured with an ultrasound machine by a member of the research team. This test does not involve any shots, radiation or invasive procedures. This will take about 1 hour. Any arrhythmia or a problem with the rate or rhythm of the heartbeat may not allow participation in this test.

### Hyperinsulinemic Euglycemic

**Clamp Study:** Insulin sensitivity will be assessed with the hyperinsulinemic euglycemic clamp as previously described in the literature. Patients will report to the GCRC the morning of the study in a fasted state. Two indwelling catheters will be inserted, one for infusion of insulin and dextrose, and another for blood sampling (Figure 2). At time zero, a fasting blood glucose measurement will be obtained, and a blood sample will be drawn to assess baseline values of inflammatory, hormonal, and oxidative stress markers. Also starting at time zero, blood samples will be drawn at 5-minute intervals

Figure 2. Clamp Study Design

for 30 minutes to assess basal levels of glucose. At 30 minutes, a prime continuous infusion of human regular insulin will be started at a rate of 2.0 mU/kg/min and maintained throughout the clamp study (about 2 to 3 hours duration). At the same time, a variable infusion of 20% dextrose will be started and will be adjusted to reach the steady-state goal of the basal blood glucose level. Throughout the clamp study, blood samples for determination of plasma glucose concentration will be drawn every 5 minutes. After steady-state conditions are achieved (dextrose infusion rate no longer being adjusted and glucose measurements consistently on target), blood samples will be drawn at 5-minute intervals for 30 minutes to assess the total body glucose disposal rate (**M-value**), the basic clamp-derived IS index, which is the average value of the glucose infusion rate during the final 30 minutes of the steady state period. The M-value will be also normalized to body weight (**Mbw**) for reasons of comparison. The mean of the plasma insulin measurements obtained at the beginning and end of the final 30-minute steady state period will be used to standardize the M-values, as the respective **M/I** indices.

We will also monitor serum potassium levels every 30 minutes and administer potassium chloride to maintain eukalemia.

Once the study is completed, the insulin infusion will be discontinued and subjects will be fed. The dextrose infusion will be gradually decreased over time with blood glucose being checked every 15 minutes. Once the blood glucose level has stabilized, the dextrose infusion will be discontinued. Standard discharge instructions will be provided to the subject by the GCRC including contact information.

**Markers of inflammation and T cell activation:** The inflammatory profile will include plasma levels of IL-17A, IFN $\gamma$ , IL-6, IL-10, and hsCRP. In addition, T cells will be isolated from 40 ml of blood and divided for two studies. One half will be subjected to flow cytometry for detection of surface markers. These will include markers for chemokine receptors, T regulatory cells, and other T cell subtypes. The remaining cells will be cultured on anti-CD3 plates at  $1 \times 10^6$  cells/ml and release of cytokines including IL-17A, IFN $\gamma$ , TNF $\alpha$ , IL-10 and IL-5 will be measured. These measures will be obtained before and after the 8-week intervention.

**Activation of monocytes and dendritic cells:** In additional experiments, we will determine if tissue sodium stores in humans, determined from  $^{23}\text{NaMRI}$  data, affects levels of isoketal-protein

adducts in human monocytes and the propensity of human monocytes to differentiate into monocyte-derived dendritic cells (MoDCs) in a chimeric NOG mouse model. We will obtain 40 ml of heparinized blood from the subjects enrolled above. Twenty subjects will be selected with high baseline sodium stores and 20 with low baseline sodium stores. The below experiments will be performed at baseline and following 8 weeks of treatment. From 10 ml of this sample, buffy coats will be isolated by centrifugation and residual RBCs lysed. Cells will be stained for CD45, CD11b, CD14, CD3, CD19, CD83 and 7-AAD (to exclude dead cells). In addition, the cells will be fixed, permeabilized, and stained for IsoK-protein adducts. We will identify monocytes as CD45+/CD11b+/CD14+ cells and determine both the percent and mean fluorescence intensity for isoKs staining. We will also examine CD19/CD83+ cells in plasma, which are circulating dendritic cells. These are a very small percent, but their level of isoketals will be of interest.

From the other 30 ml, we will sort monocytes using negative selection. Human monocytes will be adoptively transferred to NOG mice. Five days later, the NOG mice will receive either normal or 4% salt chow. One week later, aortas, spleen and lymph nodes will be harvested, single cell suspensions prepared, and samples stained as described above. We will determine the number of cells that infiltrate the aorta, spleen and lymph nodes and have converted to CD14+/CD83+ and CD14/CD83+. Because we start with a pure population of CD14+/CD83 monocytes, this transformation represents conversion to DCs. Using PCR, we will examine mRNA in the aortas for human cytokines produced by DCs that influence the inflammatory milieu, including IL-6, IL-1 $\beta$ , IL-23, TGF $\beta$  and IL-12.

#### Schedule of Procedures

Procedure	Screening	Week 0	Week 2	Week 4	Week 8
Physical exam	✓				✓
Vital signs	✓	✓	✓	✓	✓
Blood collection	✓	✓	✓	✓	✓
Pregnancy test	✓	✓	✓	✓	✓
CMP	✓	✓	✓	✓	✓
Urine collection	✓	✓	✓	✓	✓
X-ray exam	✓				
 NaMRI		✓			✓
PWV		✓			✓
HEGC		✓			✓
Hand grip test		✓			✓
Research labs		✓	✓	✓	✓
Immune cell analysis		✓			✓
Study drug/placebo dispensing		✓		✓	
Diet recalls		✓		✓	✓

## 7.0 Risks of Investigational Agents/Devices (side effects)

- Inconvenience of reporting to the GCRC.
- Eating a low salt diet for 8 weeks may be inconvenient.
- Fasting for 8 hours may be inconvenient.
- X-ray exam: For subjects who may have metal in their body, this research study involves exposure to radiation from 1 X-ray exam. The total amount of radiation that you might receive by participating in this study is equal to your body receiving 9 months of radiation from your natural surroundings, or about 5% of the amount allowed in a year for people exposed to radiation as part of their work.
- Having to lie still during the  $^{23}\text{Na}$ MRI scan may be uncomfortable.
- Aortic pulse wave velocity measurement is a non-invasive test and poses no known risks. The only inconvenience is time spent performing the test.
- The insulin infusion during the clamp study can lower blood potassium levels. If this drops too low, the subject's heart rhythm may be affected. We will closely monitor potassium levels (every 30 minutes), and place the subject on a machine that monitors the heart to decrease this risk and to observe any complications. If a decrease in potassium occurs, it will be replaced intravenously.
- Replacing the potassium may cause slight burning or irritation and the subject's heart rhythm may be affected. Again, we will monitor the subject's heart to decrease this risk and adjust the rate of replacement accordingly.
- There is a small risk of low blood sugar during the clamp study. If this occurs, the subject may experience any of these symptoms: feeling lightheaded, headache, fast heartbeat, sweating, blurred vision, hunger, and rarely seizures. We will check blood sugar every 5 minutes. If the blood sugar level drops below normal, it will be restored intravenously.
- Inconvenience of having gelled electrodes placed on the chest and being connected to a heart monitor during the clamp study. The gelled electrodes used for ECG monitoring may cause skin irritation.
- Pain, redness, soreness, bruising, or infection may occur at the needle stick site. Rarely some people faint. The study doctor may put some cream (called EMLA) on the skin to numb the area so the subject will not feel the needle stick as much. The numbing cream may make the skin or the area have a change in skin color, but this is rare.
- The study drugs may lower blood pressure excessively or alter electrolyte levels. Electrolyte imbalance may occur. We will monitor blood pressure and electrolyte levels throughout the study, and give electrolyte supplements or slightly change diet as needed. If persistent electrolyte imbalance occurs, the subject may be withdrawn from the study.
- The study drugs may produce allergic reactions. We will exclude subjects with allergies to these drugs and if allergies to these drugs develop during the course of the study, we will discontinue the subject.
- The study drugs should not be used during pregnancy. As a precaution we will exclude pregnant women. We will check urine pregnancy tests before each study day. If a woman self-reports pregnancy to us, we will immediately discontinue study medication and withdraw that subject. Risk is further minimized by the short duration of the study.

- The most commonly reported side effect of the study drugs is gastrointestinal upset (diarrhea, cramping, nausea/vomiting, etc.).
- Other less common side effects include weakness, dizziness, headache, leg cramps, and drowsiness.
- Spironolactone may produce reversible breast tenderness or enlargement in a minority of male subjects. This risk will be minimized due to the short duration of the study. Subjects have the option of withdrawing from the study if this side-effect necessitates.

As with all research studies, there are unidentifiable and unforeseeable risks that may occur during this study.

